11.5. Continuation of Treatment

There is no provision to provide study treatment after the study.

CONFIDENTIAL

The information contained herein may not be used, disclosed, or published without the written consent of
Biogen MA Inc.

12. STUDY TREATMENT MANAGEMENT

Study treatment will be manufactured, handled, and stored in accordance with applicable Good Manufacturing Practice.

Site staff should follow the DHA for specific instructions on the handling, preparation, administration, and disposal of the study treatment. The DHA should align with all other references (including the protocol).

Study treatment must be dispensed only by a pharmacist or appropriately qualified staff. Study treatment is to be dispensed only to participants enrolled in this study. Once study treatment is prepared for a participant, it can be administered only to that participant. Study treatment are for one-time use only; any study treatment remaining in the vial should not be used for another participant.

Each study treatment kit will contain 1 vial. Any additional components provided will be described in the DHA. Study treatment vials (i.e., BIIB093 or placebo) contain a white to off-white lyophilized powder for IV administration after reconstitution; vials of BIIB093 and placebo will look identical.

12.1. BIIB093

The contents of the BIIB093 label will be in accordance with all applicable regulatory requirements. The expiry or use-by date is stored in the IRT system, and printable assignment reports are available to site personnel. Study treatment should not be used after the expiration, expiry, or use-by date.

Each vial of BIIB093 contains glibenclamide 6.0 mg, mannitol 180 mg, and sodium hydroxide to adjust the pH during manufacture. Once reconstituted, study treatment is administered in 0.9% sodium chloride.

The study treatment in normal saline is stable at room temperature for 30 hours. A new vial is used for dosing on each day of the 4-day infusion.

12.1.1. BIIB093 Preparation

Study treatment will be prepared at the site by a properly qualified blinded individual according to institutional standards. The individual preparing BIIB093 should carefully review the instructions provided in the DHA. As noted previously, BIIB093 cannot be administered with PVC bags and lines due to adsorption issues. Additionally, the drug adsorbs to inline filters. Refer to DHA for additional information.

If the packaging is damaged, or if there is anything unusual about the appearance or attributes of the vials or study treatment, do not use the study treatment. The vial in question should be saved at the study site, and the problem immediately reported to Biogen.

CONFIDENTIAL

The information contained herein may not be used, disclosed, or published without the written consent of Biogen MA Inc.

Please refer to the DHA for detailed instructions regarding reconstitution of the study treatment.

12.1.2. BIIB093 Storage

Study treatment must be stored in a secure location.

All vials of BIIB093 are to be stored at 1°C to ≤ 25°C (34°F to ≤ 77°F) protected from light, in a locked location with limited access until used, in accordance with labeled storage requirements. Storage temperature must be monitored and recorded per the instructions provided in the DHA.

12.1.3. BIIB093 Handling and Disposal

The Investigator must return all used and unused vials of BIIB093 as instructed by Biogen unless approved for onsite destruction. For additional information, please refer to the DHA.

If any BIIB093 supplies are to be destroyed at the study site, the institution or appropriate site personnel must obtain prior approval from Biogen, by providing, in writing, the destruction policy or details of the method of destruction. After such destruction, Biogen must be notified, in writing, of the details of the study treatment destroyed (e.g., kit numbers, quantities), the date of destruction, and proof of destruction.

The Investigator must notify the Sponsor of any damaged or unusable study supplies that were supplied to the site.

12.1.4. BIIB093 Accountability

Accountability for study treatment is the responsibility of the Investigator. The study site must maintain accurate records demonstrating dates and amount of study treatment received, to whom dispensed (participant-by-participant accounting), and accounts of any study treatment accidentally or deliberately destroyed or lost.

Unless otherwise notified, all vials, both used and unused, must be saved for study treatment accountability. Please refer to the DHA for additional information. By the end of the study, reconciliation must be made between the amount of BIIB093 supplied, dispensed, and subsequently destroyed, lost, or returned to Biogen. A written explanation must be provided for any discrepancies.

12.2. Placebo

Placebo vials are to be stored at 1°C to ≤ 25°C (34°F to ≤ 77°F) and protected from light in a secured location with limited access. Each vial of matching placebo contains mannitol 180 mg, as well as sufficient sodium hydroxide to adjust pH during manufacture. The pH of the infusion is approximately 6 to 8.

CONFIDENTIAL

The information contained herein may not be used, disclosed, or published without the written consent of Biogen MA Inc.

13. **EFFICACY, [REDACTED] PHARMACOGENETIC, AND GENETIC ASSESSMENTS**

See Section 5 for the timing of all assessments.

13.1. **Clinical Efficacy Assessments**

NOTE: the 90- and 180-Day efficacy outcomes will be performed by personnel who are blinded to on-treatment BG levels, BG-related AEs, and carbohydrate administration (e.g., intravenous glucose or parenteral nutrition). Such persons will not have access to the participant's medical record from the acute hospitalization study period but will instead be provided with participant/family/LAR contact details (if they are required to schedule the follow-up), the source documents for the assessments to be performed, and the list of unresolved AEs for the 30-, 90-, and 180-day follow ups.

The following clinical and imaging assessments will be performed to evaluate the efficacy of BIIB093:

- NCCT/MRI Assessments
 - Total contusion volume will be assessed by the central imaging core laboratory on baseline NCCT, 24-hour NCCT, and the 96-hour scan (MRI and/ or NCCT) and the scans obtained prior to DC, IPH evacuation, or CMO.
 - Absolute hematoma volume from baseline to 24 hours (the NCCT scan closest to the 24-hour timepoint will be used) unless DC, IPH evacuation, or CMO occurred prior to 24 hours, the scan acquired just prior to these procedures will be used.
 - Absolute edema volume from baseline to 96 hours (the MRI and/or NCCT scan closest to the 96-hour timepoint will be used) unless DC, IPH evacuation, or CMO occurred prior to 96 hours, in which case the scan acquired just prior to these procedures will be used.
- [REDACTED]
- NCCT and MRI will be acquired per specifications outlined in the Imaging Manual.
- All imaging reads for efficacy will be performed by trained and certified central readers blinded to treatment assignment per procedures detailed in the Imaging Manual.
- Functional/Neurological Outcomes Assessments

CONFIDENTIAL

The information contained herein may not be used, disclosed, or published without the written consent of Biogen MA Inc.

- GCS and GOS-E
- mRS: Biogen will provide an mRS source document that outlines the procedures and key questions to ask to assess mRS (see also blinding Section 9.3). Details will be provided in the Study Reference Guide.
- mRS assessments at Day 90 and Day 180 should be conducted in person where possible, and otherwise by telemedicine or telephone call, in order of preference. The same mRS rater should follow a participant for the duration of the study whenever possible. The Day 90 and Day 180 mRS assessments may be reviewed centrally and if so, queries will be issued in the event of discrepancies or inconsistencies.

[REDACTED]

[REDACTED]

[REDACTED]

[REDACTED]

[REDACTED]

[REDACTED]

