9.3. Blinding Procedures

The Investigators, study site staff, participants, and caregivers will be blinded to the participant treatment assignments for the duration of the study. To maintain the study blind, it is imperative that subject treatment assignments are not shared with the subjects, their families, or any member of the blinded study team, both at the site and at Biogen. To ensure that efficacy and outcome assessors are blinded to study treatment, evaluators performing all efficacy and outcome evaluations will be blinded to knowledge of AEs and SAEs during the acute hospitalization phase of the study (evaluators should not have participated in the treatment during the acute hospitalization phase of the study nor review the participant's hospital records from the acute hospitalization study period including BG levels, BG management, or carbohydrate intake [e.g., intravenous glucose or parenteral nutrition]).

The study Sponsor and CRO study management team will be fully blinded for the study. Interim analysis will be performed by an independent unblinded Sponsor team whose members are not part of the study management team for the continued data collection and study management. Full treatment assignment will only be available to this independent unblinded Sponsor team.

After the last participant completes their Day 4 Visit, data for the primary endpoint and available data for the secondary endpoints will be locked for analysis. An independent unblinded Sponsor team whose members are not part of the study management team for the continued data collection and study management will perform the primary and secondary efficacy analyses. The Sponsor and CRO study management team responsible for all site interactions and data entry will remain blinded to individual treatment assignments until the final database lock. The final database lock will occur after the last participant completes their Day 180 Follow-up Visit.

At the end of the study (i.e., once the clinical study report is finalized), if unblinding will not jeopardize the results of ongoing related studies, Biogen will provide the randomization codes to Investigators, who then can inform their participants about the treatment received.

CONFIDENTIAL

The information contained herein may not be used, disclosed, or published without the written consent of
Biogen MA Inc.

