15.3. Monitoring and Recording Events

15.3.1. Adverse Events

Any AE experienced by the participant between the time of first dose of study treatment and the participant’s final clinic visit (including follow-up visit) is to be recorded on the eCRF, regardless of the severity of the event or its relationship to study treatment. At each study visit, the Investigator will assess the participant for AEs and will record any new AEs or updates to previously reported AEs on the eCRF. AEs that are ongoing when the participant completes or discontinues the study will be followed by the Investigator until the event has resolved, stabilized, or returned to baseline status. AEs ongoing at the time of the participant’s study

CONFIDENTIAL

The information contained herein may not be used, disclosed, or published without the written consent of Biogen MA Inc.

completion outcome will be recorded as ongoing on the eCRF. Serious AEs will be followed via ongoing Safety Report updates.

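### Protocol 9.3 blinds outcome evaluators to acute-phase adverse events, yet 13.1 gives the Day 90/180 raters an unresolved-AE list that can contain them

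*Protocol*

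**What the plan says.** Protocol Section 9.3 (Blinding Procedures) states that "evaluators performing all efficacy and outcome evaluations will be blinded to knowledge of AEs and SAEs during the acute hospitalization phase of the study". It gives the reason, which is to keep assessors unaware of treatment. It adds that evaluators must not have taken part in acute care or read the acute hospital record, including glucose values, glucose management and carbohydrate intake. It makes no exception for events that remain open.

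The note that opens Protocol Section 13.1 (Clinical Efficacy Assessments) assigns the Day 90 and Day 180 outcomes to "personnel who are blinded to on-treatment BG levels, BG-related AEs, and carbohydrate administration". These people are denied the acute-phase medical record, "but will instead be provided with participant/family/LAR contact details" (if needed for scheduling), together with the source documents for the assessments and "the list of unresolved AEs for the 30-, 90-, and 180-day follow ups".

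Protocol Section 15.3.1 sets the recording window for AEs. It begins "Any AE experienced by the participant between the time of first dose of study treatment" and runs to the final visit, with events still open at that point followed further. The SAP contains no rule on who rates GOS-E and mRS or on what those raters may know.

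**The concern.** GOS-E and mRS depend on an interviewer's judgement. Section 9.3 protects that judgement by keeping the rater away from what happened in hospital. A list of open AEs brings part of that history back by another route. A rater who knows of an unresolved in-hospital complication may score disability with that complication in mind. If the event points to glucose lowering, the rater may also form a view about treatment.

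The protocol itself treats such information as sensitive, since both sections take the trouble to withhold it. The endpoints are not trivial either: GOS-E at Day 180 and mRS at Day 90 are the two functional secondary endpoints, and the rationale in the Version 3 amendment summary describes Day 180 GOS-E as the registrational endpoint in TBI trials.

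**Working it through.** No sample size, power or error-rate figure is involved, so there is nothing to recompute. The check is to set the provisions side by side.

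1. **What is withheld (9.3).** All AEs and SAEs of the acute hospitalization, from all efficacy and outcome evaluators. The sentence could be parsed as a blind that lasts only while the participant is in hospital. The bracketed text that follows rules this out: it bars evaluators from the hospital record of that period, which makes sense only if the events of that period are what is being withheld.

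2. **What is withheld (13.1).** Glucose levels, glucose-related AEs and carbohydrate administration. This is narrower than 9.3, so the two sections already differ in scope.

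3. **Is 13.1 a deliberate exception to 9.3?** It does not say so. Its mRS item refers the reader back to the blinding rules in 9.3, so 13.1 relies on the rule that its own note cuts across.

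4. **Who gets the list (13.1).** The same Day 90/180 raters, in place of the acute record.

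5. **What can be on the list.** AEs are collected from the first dose (15.3.1), which falls within the acute hospitalization. An event that starts in hospital and has not resolved by Day 90 or Day 180 is an unresolved AE. Section 13.1 sets no limit by onset date, so such an event belongs on the list. Steps 1, 4 and 5 together are the conflict.

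6. **Glucose-related AEs.** Section 13.1 blinds the raters to these but does not state that they are removed from the list. The intention can be inferred; the instruction is missing.

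7. **When the list is seen.** Not stated. It is named in the same sentence as the source documents for the assessments, which makes receipt at or before the visit plausible, but no order relative to scoring is given.

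8. **Which endpoints are exposed.** Protocol Section 6 names mRS at Day 90 and GOS-E at Day 180 as secondary endpoints. In the schedule of activities, mRS is not assessed at Day 30. The primary endpoint is a volume read by central readers blinded to assignment (13.1 and 19.1.5), who are not the people given the list.

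9. **Carry-over.** Sections 13.1 (for mRS) and 13.5 ask that the same rater follow a participant where possible. Something learned from the list at one visit can therefore still be known at the next.

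**The case against.** The strongest defence has four parts.

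- **The list has a purpose.** AE review is scheduled at Days 30, 90 and 180, and someone must know which events are open. This explains the provision but does not reconcile it with 9.3. Section 15.3.1 gives AE assessment at each visit to the Investigator, so the outcome rater need not be the one holding the list.
- **Section 13.1 can be read in harmony with itself.** Having blinded the raters to glucose-related AEs, it presumably means the list to respect that. This is fair. A reader might infer that hypoglycemia events will be shown to raters; the documents do not support that. The fault is an unstated step, not a demonstrated disclosure.
- **Treatment is unlikely to be revealed.** A reader might infer that the list unblinds raters. Hypoglycemia is the only adverse drug reaction identified (Section 4.3.3), so an open event of another kind does not obviously point to an arm. After treatment for low glucose, readings are repeated every 15 minutes until three in a row reach at least 80 mg/dL (Section 11.4.1.1.1). An episode itself would hardly be open at Day 90, and only a lasting consequence could be. This largely stands. What remains is anchoring, and some open deficits would emerge in the interview anyway.
- **Operational detail sits elsewhere.** The mRS source document and the Study Reference Guide may set the order of scoring and AE review. They are not available here. A reader might infer that raters see the list before scoring, but the protocol does not say so. Equally, an instruction in those documents would not cure two protocol sections that disagree.

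**Conclusion.** The inconsistency is real but limited. Following 13.1 as written can disclose to Day 90/180 raters acute-phase AEs that 9.3 says they must not know, and nothing in the protocol or SAP resolves this. It concerns acute-onset events that remain open at follow-up. Events that resolved in hospital would not be listed.

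The exposure is confined to judgement-based outcomes, namely mRS at Day 90 and GOS-E at Day 180 among the secondary endpoints. It would be wrong to extend it to the primary endpoint, or to speak of both secondary endpoints at every follow-up visit.

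The documents give no rate of unresolved acute AEs and no estimate of rating bias, so no magnitude can be calculated. That the effect is small is a judgement resting on two assumptions: most hypoglycemia resolves well before Day 90, and other open events carry little information about treatment. On that footing this is a desirable clarification, not a threat to the trial's conclusions.

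**What to change.** Reconcile Sections 9.3 and 13.1 with wording in 13.1, repeated in the Study Reference Guide:

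- At each follow-up visit, GOS-E and mRS (where scheduled) are scored and entered before the rater opens any list of unresolved AEs.
- Any list given to a rater omits glucose-related AEs. Those still open are followed by site staff who are not rating outcome.
- Where a site already has other staff recording AEs, they hold the list and the rater does not receive it. This is the better arrangement where available, because scoring first protects only the current visit and the same rater may return knowing what was listed.

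The cost is protocol or guide wording and a minor change in the order of the visit, with no added visits or data. Moving the list to other staff is proposed only where they are already in place. At sites where one person does both tasks, the score-first rule applies, leaving some carry-over to later visits.

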13.4. Pharmacogenetic and Genetic Assessments

Where allowed by local, regional, and national regulatory authorities and ethics committees, participants will be offered the option to participate in genetic research related to brain contusion and metabolism of BIIB093. This is a 1-time optional blood draw. Participants, or the participant's LAR, will be required to sign a separate ICF between the start of study and hospital discharge. The pharmacogenetic sample should be collected as close to obtaining consent as possible and preferably within 24 hours of the start of study treatment to minimize the influence of participant outcomes on obtaining consent.

Genetic polymorphisms in genes associated with brain contusion or drug absorption, distribution, metabolism, and elimination (including but not limited to ABCC8, CYP2C9, OATP1B1, and G6PD) could influence the observed safety and efficacy of BIIB093. Genes of downstream pathways may also be explored. Despite continuing advances in genetic research and the

CONFIDENTIAL

The information contained herein may not be used, disclosed, or published without the written consent of
Biogen MA Inc.

[figure not shown]
understanding of brain contusion, not all genetic factors relevant to BIIB093 have been identified.

The DNA samples will be coded with the participant's identification number and stored for 15 years or a duration dictated by local, national, or regional laws or regulations. No genotyping or genetic data will be provided to the participant. Details on genetic sample collection will be provided in a separate laboratory manual.

Other genetic tests for additional safety measures may be conducted where applicable (see Section 14.2).

13.5. Other Assessments: Patient Outcome Measures

Complete instructions for outcomes measure assessments will be provided separately. Raters must be trained and qualified to perform any assessment and meet the guidelines outlined in the Study Reference Guide. To eliminate inter-rater bias, the same rater should follow a participant whenever possible for the duration of the study.

CONFIDENTIAL

The information contained herein may not be used, disclosed, or published without the written consent of Biogen MA Inc.

14. SAFETY ASSESSMENTS

[figure not shown]
See Section 5 for the timing of all safety assessments.

14.1. Clinical Safety Assessments

The following clinical assessments will be performed to evaluate the safety profile of BIIB093:

- Medical history
- Physical examinations, including weight and height (may be estimated)
- Vital sign measurements: temperature, pulse rate, systolic and diastolic blood pressure, respiratory rate, and oxygen saturation
- 12-lead ECGs
- Concomitant therapy and procedure recording

All medications, including but not limited to dextrose solutions, osmotherapy, paralytics, sedatives, and vasoactive drugs used through Day 180 are to be recorded in the eCRF. Concomitant procedures will be recorded through Day 180.

- AE and SAE recording
- Assessment of suicidal ideation/behavior at Screening and follow-up in patients whose level of consciousness is compatible with completion of the abbreviated suicidal ideation/behavior questionnaire. Investigators should use their best judgment to identify patients suitable for this assessment.

14.2. Laboratory Safety Assessments

Samples will be analyzed using Good Laboratory Practice-validated assays.

The following laboratory assessments, in accordance with the schedule of activities, will be performed to evaluate the safety profile of BIIB093. All assessments will be performed at a local laboratory where possible.

- Hematology: complete blood count and platelet count, and absolute neutrophil count
- Blood chemistry: albumin, creatinine, blood urea nitrogen, glucose, calcium, phosphorus, bicarbonate (if available), chloride (if available), sodium, and potassium

CONFIDENTIAL

The information contained herein may not be used, disclosed, or published without the written consent of
Biogen MA Inc.

- Liver function test: bilirubin (total and indirect), alkaline phosphatase, ALT, AST, and gamma-glutamyl transferase
- Coagulation panel (INR, PTT, fibrinogen)
- Note that in any case of confirmed hemolytic anemia after randomization, the required local standard tests should be performed to confirm etiology of disease, including a G6PD genetic or enzymatic test (in accordance with local practice).

